Memantine (Mem) is a voltage-dependent, non-competitive N-methyl-D-aspartate (NMDA) receptor antagonist that inhibits the activity of ionotropic glutamate receptors (iGluRs)^[12]. It is used as a first-line treatment for moderate to severe Alzheimer's disease, with a good safety profile and patient tolerance^[13]. Notably, preclinical studies conducted by [name]'s team have shown that memantine effectively reduces the incidence of AF induced by three different pathophysiological conditions (stretch-induced, cholinergic, and ischemic AF) in isolated rat hearts in a concentration-

dependent manner. In *in vivo* experiments, memantine effectively prevented and terminated AF induced by three different pathophysiological conditions (aortic constriction, acetylcholine, and hypoxia) in rats. The primary mechanism of action is that memantine blocks glutamate currents in atrial myocardial cells, reducing calcium leakage, and effectively reducing trigger activity, delayed afterdepolarization, and ectopic beats, thereby reducing AF triggers and effectively preventing AF. Additionally, memantine significantly decreased the number of reentrant circuits in the atrial myocardium, thus effectively terminating AF. Furthermore, memantine was shown to reduce the incidence of AF-like abnormal electrophysiological events and delayed afterdepolarization in human-induced pluripotent stem cell-derived atrial myocardial cells (iPSC ACMs), suggesting that this drug may also exert electrophysiological regulatory effects on human myocardial cells. Previous animal and clinical studies have demonstrated that memantine has a favorable safety profile, reducing the occurrence of reperfusion arrhythmias and slowing heart rate without prolonging the QT interval [15-17], thus not increasing the risk of torsades de pointes. Based on these findings, we hypothesize that memantine may be an ideal treatment for rapid atrial arrhythmias. The repurposing of an existing drug significantly shortens the drug development timeline and reduces research costs. Therefore, this study aims to explore the efficacy and safety of memantine in patients with frequent PACs.

2. Study Objectives and Endpoints

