2.2.2 Safety Endpoints

The incidence of AEs (including psychiatric symptoms, seizures, bradycardia and new-onset heart failure, etc.), SAEs, laboratory test abnormalities, and abnormal ECG findings.

3. Study Design

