5.8 Management of Intolerable PAC-Related Symptoms

If a participant develops severe, intolerable symptoms attributable to frequent PACs, the investigator may initiate adjunct therapy with the cardio-selective β -adrenergic blocker bisoprolol fumarate (5-mg per tablet). Treatment should start at 2.5 mg once daily (qd) and may be titrated, on the basis of heart rate and symptom control, to a maximum of 10 mg qd. Except under these circumstances, the use of class I–IV antiarrhythmic agents or any herbal/traditional Chinese medicines with antiarrhythmic properties is prohibited during the trial.

6. Study Procedures and Visit Schedule

The trial is divided into three phases: a screening period (Visit 1, V1), a treatment period (Visits 2–4, V2–V4), and a follow-up visit (Visit 5, V5). Participants will attend all visits as outlined in the protocol. Any AE occurring during the study will be followed until the event resolves, stabilizes, or the participant is lost to follow-up.

An overview of scheduled activities is provided in the study-flow diagram, and detailed requirements for each assessment are listed in Table 2. For participant safety, the investigator may increase the frequency of scheduled assessments or add unscheduled

assessments not specified in the flow diagram whenever clinically warranted (e.g., in response to an AE).

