12-lead ECG	Heart rate, P-R interval, QRS wave duration, Q-Tc interval (calculated by Bazett's formula), presence of AFL, presence of AF, presence of atrioventricular block
Blood or urine pregnancy	Blood/urine human chorionic gonadotropin, fertile women only. For infertile women, please note the reason, e.g. menopause \geq 1 year, hysterectomy, sterilization, etc.
Laboratory tests	
 ➤ Routine blood count: white blood cell count, neutrophil ratio and count, lymphocyte ratio and count, red blood cell count, hemoglobin amount, red blood cell pressure volume, platelet count ➤ Liver function: alanine aminotransferase, glutamine aminotransferase, gamma glutamyl transpeptidase, total bilirubin, direct bilirubin, indirect bilirubin. ➤ Thyroid function: fT3, fT4, TSH; ➤ Renal function: creatinine, urea nitrogen or urea, glomerular filtration rate; ➤ Electrolytes: blood sodium, blood potassium, blood magnesium, blood calcium ➤ Lipids: total cholesterol, triglycerides, HDL cholesterol, LDL cholesterol esters ➤ Fasting glucose, glycosylated hemoglobin, NT-pro BNP (preferred) or BNP ➤ Urine PH
Ambulatory electrocardiograph monitoring	
 ➤ 24-hour average number and load of PACs, 24-hour average number and load of bouts of NSAT, 24-hour average episodes count of NSAT, SAT, AF, AFL ➤ Monitoring start time and end time, monitoring duration
Cardiac ultrasound	
 ➤ Left atrial internal diameter (mm), septal thickness (mm), left ventricular end-systolic internal diameter (mm), left ventricular end-diastolic internal diameter (mm), left ventricular ejection fraction (LVEF %)

Inspection item	Requirements and observables
NYHA Cardiac Function Classification	➤ Class I, II, III, IV

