4.3.4 Vital Signs

Analysis population: SS

Parameters: Body temperature, heart rate, respiratory rate, systolic and diastolic blood pressure

Observed values and change-from-baseline data will be summarized as described above. Baseline-to-worst shift tables (Normal/NCS/CS) will be compiled using the same severity hierarchy.

4.3.5 12-Lead ECG

Analysis population: SS

Parameters: Heart rate, PR interval, QRS duration, QT and QTc intervals

For each scheduled visit, observed values and change from baseline will be summarized. Each tracing will be classified as Normal, NCS, or CS, and baseline-to-worst shift tables will be generated (scheduled + unscheduled recordings).

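### QTc is specified by Bazett's formula only, for a drug the protocol describes as rate-slowing; if heart rate falls on memantine, a QTc increase could be partly or fully hidden

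*Protocol*

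**What the plan says.** **Correction formula.** Protocol Table 5 (section 6.1) lists what is read from the 12-lead ECG. It begins with "Heart rate, P-R interval, QRS wave duration" and continues with the "Q-Tc interval (calculated by Bazett's formula". Uncorrected QT is not in that list.

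**Analysis.** SAP 4.3.5 gives "Parameters: Heart rate, PR interval, QRS duration, QT and QTc intervals" and states: "For each scheduled visit, observed values and change from baseline will be summarized". It also classes each tracing as normal, abnormal not clinically significant or abnormal clinically significant, for baseline-to-worst shift tables. It names no QTc formula, so Table 5 governs by default. It sets no QTc threshold, outlier category or between-group test, and Protocol 7.3.7.2 likewise keeps ECG results descriptive.

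**Why heart rate may move.** The Background (Protocol section 1) credits earlier animal and clinical studies with showing memantine "slowing heart rate without prolonging the QT interval", and infers that torsades risk is not raised. The safety endpoints (Protocol 2.2.2) cover "AEs (including psychiatric symptoms, seizures, bradycardia and new-onset heart failure, etc", and also "laboratory test abnormalities, and abnormal ECG findings". Protocol 5.8 permits a beta-blocker in either arm for intolerable symptoms, which "may be titrated, on the basis of heart rate and symptom control".

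**The concern.** Bazett divides QT by the square root of RR. If QT actually changes with RR less steeply than that, the division over-adjusts as RR lengthens, and corrected QT drifts down as the heart slows. A drug that slows the heart and modestly prolongs repolarisation could then show little or no change in Bazett QTc.

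The protocol itself presents memantine as rate-slowing and QT-neutral. A correction that falls with slowing cannot cleanly test the second property when the first is present. The QTc summaries could be affected and, so far as readers rely on the recorded QTc, so could the shift tables. The primary endpoint, the testing hierarchy and the power are not touched.

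**Working it through.** The plan states no figure for this point, so there is nothing of its own to reproduce.

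**Inputs from the documents:** Bazett as the only named formula (Protocol Table 5); memantine described as slowing heart rate, with no size given (Protocol Background); heart rate, QT and QTc summarised (SAP 4.3.5).

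**Inputs assumed, because the documents give none:** baseline heart rate 75 bpm (range 60 to 90); slowing of 2 to 15 bpm; rate-corrected QT of 400 ms; true QT-RR exponent b of 1/3, with 0.40 and 0.50 as alternatives.

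**Formulas.** RR = 60/HR in seconds. QT = 400 × RR^b. Bazett QTcB = QT/RR^0.5 = 400 × RR^(b - 0.5). The artefact is QTcB at the slower rate minus QTcB at 75 bpm, with no drug effect on repolarisation.

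**Step 1: artefact with no true change, b = 1/3.** At 75 bpm, RR = 0.800 and QTcB = 400 × 0.800^(-1/6) = 415.2 ms.

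| Slowing | HR | RR | QTcB (ms) | Artefact (ms) |
|---|---|---|---|---|
| 2 bpm | 73 | 0.822 | 413.3 | -1.9 |
| 5 bpm | 70 | 0.857 | 410.4 | -4.7 |
| 10 bpm | 65 | 0.923 | 405.4 | -9.8 |
| 15 bpm | 60 | 1.000 | 400.0 | -15.2 |

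**Step 2: sensitivity.** At b = 0.40 from 75 bpm, the same slowings give -1.1, -2.8, -5.8 and -9.0 ms. For 10 bpm slowing across baselines of 60 to 90 bpm, the artefact runs from -12.0 to -8.3 ms at b = 1/3 and from -7.2 to -4.9 ms at b = 0.40. At b = 0.50 it is 0. A rate increase reverses the sign: at b = 1/3 from 75 bpm, +4.5 ms for 5 bpm faster and +8.8 ms for 10 bpm faster.

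**Step 3: a true increase of 10 ms.** Replace 400 by 410 after treatment (b = 1/3, from 75 bpm). QTcB then shows +10.4 ms with no slowing, +8.5 at 2 bpm, +5.5 at 5 bpm, +0.3 at 10 bpm and -5.2 at 15 bpm.

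**Step 4: does uncorrected QT rescue the reading?** Baseline QT is 400 × 0.800^(1/3) = 371.3 ms. Slowing by 10 bpm with no drug effect gives 400 × 0.923^(1/3) = 389.5 ms, a rise of 18.1 ms. Slowing by 5 bpm with a true 10 ms effect gives 410 × 0.857^(1/3) = 389.5 ms, also a rise of 18.1 ms. Uncorrected QT alone cannot tell these cases apart; it has to be read with heart rate.

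**Step 5: the alternative.** Fridericia is QTcF = QT/RR^(1/3). If b = 1/3 its artefact is 0 by construction. If b = 0.40, 10 bpm slowing gives 400 × (0.923^0.067 - 0.800^0.067) = +3.8 ms, against -5.8 ms for Bazett. If b = 0.50, Bazett is exact and Fridericia gives 400 × (0.923^(1/6) - 0.800^(1/6)) = +9.3 ms. Fridericia is therefore the less rate-dependent choice when b is nearer 1/3 than 1/2, and where it errs under slowing, it errs towards showing an increase.

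**The case against.** The strongest reply is that little turns on this. ECG results are descriptive. No QTc eligibility limit, stopping rule, threshold or test exists, and SAP 4.3.5 reports heart rate and uncorrected QT by visit beside QTc. QT can also be recovered from Bazett QTc and heart rate, so another correction can be derived at any time. All of that stands, and it confines the consequence to how the safety tables are read. It does not remove the problem, since Step 4 shows that uncorrected QT mixes rate and drug effects.

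Three stronger readings are tempting, and the documents support none of them:

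- *Bazett will hide QTc prolongation.* The documents give no baseline rate, rate change or QT-RR exponent. The Background credits animal and clinical work jointly, and listing bradycardia as an event to watch does not establish a mean shift between arms. A slowing of 2 bpm would hide only about 2 ms.
- *Bazett QTc is the only repolarisation measure.* It is the only rate-corrected one; SAP 4.3.5 also lists uncorrected QT.
- *Beta-blocker rescue adds to the bias in memantine's favour.* Rescue is open to both arms. If memantine reduces symptoms, rescue could fall more on placebo, lower QTcB there and make memantine look worse. The direction is undetermined.

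**Conclusion.** The point holds as a conditional one. The plan fixes a single, rate-dependent QTc correction for a drug that the protocol describes as slowing heart rate. If the rate falls on memantine and QT follows RR less steeply than a square root, Bazett QTc could partly or fully hide an increase: about 2, 5 or 10 ms for 2, 5 or 10 bpm slowing under a cube-root relation from 75 bpm, roughly 60% of that at an exponent of 0.40 (5.8/9.8 at 10 bpm), and nothing under a square-root law. A rate increase, or rescue concentrated in placebo, would push the comparison the other way. These sizes rest on assumed values, not on anything in the documents. It would be wrong to infer that the trial's efficacy result, or any decision rule, is at risk. The matter is one of descriptive safety interpretation and is worth correcting because correction is cheap.

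**What to change.** In SAP 4.3.5:

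- Name Fridericia QTc as the main rate-corrected value. Compute it from QT and heart rate, or, where only Bazett QTc and heart rate are held, as QTcF = QTcB × RR^(1/6).
- Keep Bazett QTc alongside, for continuity with Protocol Table 5 and because Fridericia is not free of rate dependence either.
- Present both next to heart-rate change, by arm and visit.
- Reconcile Table 5, which does not list uncorrected QT, with SAP 4.3.5, which summarises it.

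The cost is one extra derived variable and one extra table. No new ECGs are needed, and no change to participant management is involved.

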6.2 Study Procedure

6.2.1 Screening Period (Visit 1)

Informed consent. Written informed consent must be obtained before any study-specific procedure performed.

Medical interview and data collection.

Demographics: age, sex, height, weight, waist circumference, race/ethnicity, and highest educational level.

Medical history: past and current illnesses (within 6 months before screening), allergy history, smoking and alcohol use, prior non-drug cardiac interventions (e.g., percutaneous coronary intervention, coronary-artery bypass grafting, catheter ablation), participation in clinical trials, concomitant medications, and prior surgeries.

Physical examination.

Vital signs: pulse, respiratory rate, blood pressure, and body temperature.

NYHA functional class.

Laboratory and diagnostic tests.

Complete blood count.

Urine pH.

Serum or urine human chorionic-gonadotropin (hCG) test, as appropriate.

Standard 12-lead ECG.

Health-related quality-of-life assessment using the SF-36 questionnaire.

Baseline ambulatory ECG.

Candidates who meet the above criteria undergo 72-hour continuous patch-based ECG monitoring to quantify PACs and confirm eligibility. Randomization is based on these data.

Randomization and study materials.

Eligible participants are randomized, then provided with study medications and diaries.

Ambulatory ECG data points.

The 72-hour recording captures:

24-hour mean PAC count and burden.

24-hour mean number and burden of NSAT episodes.

Episodes of SAT, AF, and AFL.

Incidence of new-onset SAT, AF, or AFL during any 72-hour recording window.

Any AE identified during screening is followed until it resolves, stabilizes, or the participant is lost to follow-up.

6.2.2 Treatment Phase

Day 1 (D1) marks the initiation of study drug administration. Participants will self-administer the investigational product per the dosing regimen described in Section 6.2 and will attend all protocol-specified visits.

The treatment phase consists of three scheduled visits:

- **Visit 2 (Day 7 ± 2 days; telephone)** — Evaluate treatment adherence, review AEs, and document concomitant medications.
- **Visit 3 (Day 28 ± 3 days; on-site)** — Conduct a clinical assessment and initiate 72-hour continuous patch-based ambulatory ECG monitoring.
- **Visit 4 (Day 42 ± 3 days; on-site; end of treatment)** — Perform a clinical assessment and repeat 72-hour ambulatory ECG monitoring.

All procedures will be conducted in strict accordance with the protocol to ensure consistent safety and efficacy assessments.

6.2.3 Follow-up Phase

A single post-treatment follow-up visit will be conducted on Day 56 ± 3 days. All evaluations will be performed in accordance with the study-flow schedule.

7. Statistical Analysis

7.1 Sample-Size Determination

In our preliminary exploratory single-arm study, memantine produced a 75.4 % mean reduction in 24-hour PAC burden. Considering the robustness of results from the small-sample trial and potential sampling error, the present trial conservatively assumes a 50 % reduction in the memantine group and a 30 % reduction in the placebo group, with a common standard deviation of 35 %. Factoring in a 15 % dropout rate, a one-sided α level of 0.025, and a 1:1 randomization ratio, a sample-size calculation performed with

EAST software (version 6.5) indicates that 256 participants (128 per group) will provide >95 % statistical power to detect the prespecified between-group difference.

7.2 Analysis Sets

Full Analysis Set (FAS) — Includes all randomized participants who receive at least one dose of investigational product; analyzed in the treatment groups to which they were randomly assigned (intention-to-treat principle).

- **Per-Protocol Set (PPS)** — Includes all randomized participants who received at least one dose of investigational product, underwent at least one post-baseline efficacy assessment, and had no major protocol deviations that could affect evaluation of the primary efficacy endpoints.
- **Safety-analysis-set (SS)** — Includes all randomized participants who received at least one dose of investigational product; safety endpoints are analyzed according to the treatment actually received.

7.3 Analysis Plan

7.3.1 Statistical Hypothesis

The primary efficacy endpoint is the percentage change from baseline to Week 6 in the 24-hour mean count of PACs.

- **Null hypothesis (H_0)**: The mean percentage reduction in the memantine group is \leq the mean percentage reduction in the placebo group.
- **Alternative hypothesis (H_1)**: The mean percentage reduction in the memantine group is $>$ the mean percentage reduction in the placebo group.

These hypotheses will be tested at a two-sided α of 0.05.

7.3.2 General principles

- **Continuous variables** will be summarized by the number of observations (n), mean, standard deviation, median, minimum, and maximum values.
- **Categorical variables** will be summarized by the number of observations (n) and corresponding percentage. Unless otherwise specified, all percentages will use the relevant analysis-population denominator.

Comprehensive statistical methods are detailed in the Statistical Analysis Plan (SAP), which will be finalized before database lock. This protocol provides only an overview of the planned analyses; in the event of any discrepancy, the SAP will take precedence.

7.3.3 Study Disposition and Participant Flow

The number and percentage of participants who were screened, experienced screen failure, were randomized, received at least one dose of study medication, and completed the trial will be summarized. Principal reasons for treatment discontinuation and/or study withdrawal will be tabulated according to the categories recorded in the electronic case-report form (eCRF). Final counts for each analysis population will also be provided.

7.3.4 Demographics and Baseline Characteristics

Demographic and baseline variables will be summarized descriptively for each treatment group. Key parameters will include (but are not limited to) age, sex, race/ethnicity, body-mass index, relevant medical history, and previous therapies. All summaries will be performed on the FAS.

7.3.5 Medication Adherence

(1) Study-drug exposure and adherence will be described for each treatment group using descriptive statistics.

(2) Concomitant medications will be tabulated and analyzed as appropriate.

7.3.6 Efficacy Analyses

All efficacy evaluations will be conducted on the FAS.

- **Primary endpoint** — The between-group difference in the percentage change from baseline to Week 6 in 24-hour PAC burden will be estimated, and the mean difference will be presented with its two-sided 95 % CI.
- **Key secondary endpoints** — These variables will be tested sequentially according to a fixed-sequence procedure to control the family-wise type I error rate.
- **Other secondary endpoints** — All remaining secondary variables will be summarized descriptively.

7.3.7 Safety Analysis

7.3.7.1 Adverse-Event Analyses

All AEs will be coded using the MedDRA and classified by SOC and PT. The analysis will focus on treatment-emergent adverse events (TEAEs)—events that first occur or worsen after the initial dose of study drug. Unless otherwise specified, AE denotes TEAEs throughout this section.

- Overall incidence — For each treatment group, the number of participants (n) and proportion (%) with any TEAE, SAE, or AE leading to death will be summarized.
- Incidence by SOC and PT — TEAEs, SAEs, and fatal events will also be tabulated by SOC and PT, with counts and percentages reported for each group.

7.3.7.2 Other Safety Assessments

Additional safety parameters—such as clinical laboratory results, vital signs, and 12-lead ECG findings—will be summarized descriptively.

7.3.8 Multiplicity Adjustment

If the primary endpoint is statistically significant (two-sided $P < 0.05$), key secondary endpoints will be evaluated with a fixed-sequence testing procedure to preserve the family-wise type I error rate. Each endpoint will be tested at a two-sided α of 0.05, and testing will proceed down the hierarchy only while significance is maintained.

Testing Hierarchy

- (1) Week 6 responder rate for PACs ($\geq 50\%$ reduction).
- (2) Change from baseline to Week 6 in NSAT burden.
- (3) Cumulative incidence of new-onset AF from baseline through Week 8.
- (4) Incidence of new-onset AF at Week 4.
- (5) Incidence of new-onset AF at Week 6.
- (6) Incidence of new-onset AF at Week 8.

If any endpoint fails to achieve significance, formal hypothesis testing will stop, and all remaining secondary endpoints will be summarized descriptively.

7.3.9 Handling of Missing Data

Primary Endpoint. Missing Week 6 24-hour PAC counts will be imputed by a prespecified multiple-imputation procedure, as detailed in the SAP.

Sensitivity Analyses. Robustness analyses for the imputation model will be described in the SAP.

Secondary Efficacy and Safety Endpoints. No imputation is planned; analyses will be performed on observed data only.

8. Safety Evaluation

8.1 Definitions

8.1.1 AEs

An AE is any untoward medical occurrence in a participant who has received the investigational product. Manifestations may include clinical signs or symptoms, new illnesses, or clinically significant laboratory abnormalities, irrespective of an established causal relationship with the study drug.

Because pre-dose safety information provides essential context for interpreting on-treatment findings, AE recording begins at the signing of the informed-consent form. These data establish the participant's baseline status and assist in determining whether subsequent events are study related.

TEAE is an AE that first appears—or an existing event that worsens in severity—after the initial dose of study medication. Unless otherwise noted, the term *AE* in this protocol refers to TEAEs.

8.1.2 Serious Adverse Events (SAEs)

An SAE is any untoward medical occurrence that, after administration of the investigational product, satisfies one or more of the following criteria:

(1) Results in death

Death is an outcome and should not be used as the event term.

If the death is sudden and the cause is initially unclear, report the event as “sudden unexplained death.” Continue follow-up until the cause is established; once confirmed, update the SAE term to reflect the specific cause of death.

(2) Is life-threatening

The participant was, at the time of the event, at immediate risk of death; events that could have become life-threatening if they had progressed are not included.

(3) Requires inpatient hospitalization or prolongation of existing hospitalization

Hospitalization (or extension of an existing stay) is not classified as an SAE if it meets any of the following conditions:

Inpatient stay < 12 hours.

Admission planned before the first study dose (e.g., elective surgery or a protocol-mandated procedure).

Admission unrelated to an AE (e.g., social or respite care).

Elective admission for treatment of a pre-existing condition that has not worsened relative to baseline.

Note: Any SAE that otherwise meets serious criteria and occurs during such a hospital stay must still be reported.

(4) Results in persistent or significant disability/incapacity

A substantial disruption in a participant's ability to conduct normal daily activities.

(5) Results in a congenital anomaly or birth defect

(6) Other medically important events

Events that may not immediately result in death, be life-threatening, or require hospitalization but, in the investigator's judgment, could jeopardise the participant or require medical or surgical intervention to prevent one of the outcomes listed above.

Examples include emergency treatment for severe bronchospasm, seizures managed outside the hospital, clinically significant cachexia, or the development of drug dependence or addiction.

